Clarification Memorandum # 1 for:

IMPAACT P1108

A Phase I/II, Open-Label, Single Arm Study to Evaluate the Pharmacokinetics, Safety and Tolerability of Bedaquiline (BDQ) Given in Combination with an Individualized Rifampin-Resistant Tuberculosis (RR-TB) Therapy in Infants, Children, and Adolescents with RR-TB Disease, Living with or without HIV

Version 2.0, dated 21 September 2022

**DAIDS Study ID #11884
IND #131,832 Held By DAIDS**

Clarification Memorandum Date: 29 March 2023

Summary of Clarifications and Rationale

This Clarification Memorandum (CM) serves to clarify terminology for the study analyses related to BDQ dosing.

Implementation

Institutional Review Board/Ethics Committee (IRB/EC) approval of this CM is not required by the study sponsor prior to implementation; however, sites may submit it to IRBs/ECs for their information or, if required by the IRBs/ECs, for their approval prior to implementation. This CM and any applicable IRB/EC correspondence should be maintained in site essential document files for IMPAACT P1108. The clarifications included in this CM will be incorporated into any future amendment of the IMPAACT P1108 protocol.

As indicated in protocol Section 10.2, interim pharmacokinetic (PK) analyses will be performed during study implementation to select BDQ doses for each cohort. Thereafter, PK modeling will be used to determine a final recommended BDQ dose for each cohort. The final recommended BDQ dose may or may not have been selected for a given cohort. Regardless of the final recommended dose, primary safety data analyses will be based on the BDQ dose selected for each cohort during study implementation, which is referred to as the final implemented dose. Protocol Sections 9.6.1 and 9.6.2.1 are modified to clarify that primary safety data analyses will be based on implemented doses. Additions to the text are indicated in bold; deletions are indicated by strikethrough.

1. Section 9.6.1, Primary Safety Analyses, first paragraph:

The primary safety analyses will focus on the 24-week time period during BDQ treatment and will include only participants whose total exposure to BDQ ~~has been~~ was at the final ~~BDQ dose~~ ~~recommended~~ **implemented dose** for their cohort for the protocol-specified period of BDQ administration. Participants who have been removed from treatment, or who have had their doses reduced as part of cohort management due to toxicities, will be included and treated as safety failures in the primary safety analysis (note that such participants may have to be excluded from any

secondary analyses which require complete follow-up at the optimal dose). Participants whose doses have been adjusted on the basis of PK results will be excluded from these primary analyses, regardless if the participant initiated BDQ at the final ~~recommended~~ **implemented** dose, and sensitivity analyses performed in an attempt to determine whether the exclusion of these participants creates a selection bias which impacts upon any results. These primary analyses will be performed after the last participant of the last cohort has completed the study drug regimen over the 24-week dosing period.

2. *Section 9.6.1, Primary Safety Analyses, fourth paragraph:*

In addition, if possible, a primary evaluation of safety across the 24 weeks of study treatment will be performed on the data from participants who have been started at the final recommended dose for a given cohort and have remained on that dose for the 24-week period or have left the study or had a dose modification due to safety failure prior to 24 weeks of exposure (in which case the participant will be analyzed as a failure). Note that such an analysis may not be possible, since the PK modeling procedure which will determine the final recommended dose will not guarantee that an adequate number of participants be on that dose. However, secondary safety analyses will include all safety data collected from first participant exposure to the end of the study, with results broken down by dose. This will include data representing the final **implemented** dose for each cohort, as well as data gathered during the dose finding stage, which may represent exposure to doses which have failed.

3. *Section 9.6.2.1, Safety, first paragraph:*

The 24-week analyses described above for the primary analysis will be repeated as secondary analyses at 72 weeks after BDQ discontinuation and by HIV status. Of note, precision may be limited for participants living with HIV, particularly if only the required minimum number of participants living with HIV are enrolled. In addition, descriptive and exposure-related analyses will present safety data from participants whose doses have undergone individual adjustment or who were treated on doses other than the final ~~recommended~~ **implemented** dose for their cohorts.

1.1 Purpose

This Primary Statistical Analysis Plan (SAP) describes the analysis plan for the primary and secondary outcome measures (except for the primary and secondary PK outcome measures) and additional outcome measures of the IMPAACT P1108 study that will be included in the primary manuscript(s). The Pharmacokinetic (PK) Statistical Analysis Plan (PK SAP) is a separate document prepared by the study pharmacometrists and will describe the analysis plan for the PK primary and secondary outcome measures. The Primary SAP outlines the general statistical approaches that will be used in the analysis of the study. It has been developed to facilitate discussion of the statistical analysis components among the protocol team, and to provide agreement between the protocol team and statisticians regarding the statistical analyses to be performed and presented in the primary analysis report. It also describes the results for the primary safety outcome measures and secondary outcomes measures (except for the PK secondary outcome measures) that will be posted on ClinicalTrials.gov.

Detailed outlines of tables, figures, and coding descriptions that will be included in the Analysis Reports are included in the Analysis Implementation Plan (AIP). There will be two Analysis Reports that will be prepared. The Primary Analysis Report will focus on the primary safety outcome measure and will be generated once the last participant has completed the Week 24 study visit and all data queries have been resolved. Analyses for the Secondary Analysis Report will address all secondary outcome measures, except for the PK outcome measures, and will be finalized once the last participant has completed the Week 96 study visit, all data queries have been resolved, and the study database closure/data lock has been completed. Outlines of analyses for exploratory objectives and outcome measures not included in the Primary SAP will be provided in a separate SAP.

1.2 Version History

The original version of the SAP was updated (V 1.1) to account for Letter of Amendment (LoA) #2, dated 28 February 2019, and LoA #3, dated 17 October 2019, for Protocol Version 1.0, dated 3 March 2016, and included updates to the Bedaquiline (BDQ) dosing regimen for all cohorts, as was determined by population PK modeling performed based on PK data for the first 12 evaluable participants in Cohort 1 (consistent with protocol Sections 3.2 and 10.2.3). In addition, this version also accounts for Clarification Memorandum (CM) #6, dated 1 April 2020, which provided guidance to sites for conducting study visits and procedures during the COVID-19 pandemic and recommended prioritization for conduct of clinically and scientifically important evaluations.

The next version 1.2 accounted for LoA # 4 dated 27 June 2022, which incorporated contents of protocol CM #6 that provided operational flexibility for conducting study visits and procedures when needed and to prioritize the conduct of clinically and scientifically important evaluations when possible. Consistent with the instructions provided in CM #6, implementation of this LoA is expected to be time-limited in relation to the COVID-19 pandemic.

Version 2 reflected updates based on Protocol Version 2.0, dated 21 September 2022, with CM #1, dated 29 March 2023.

This current version just notes the version change based on LoA #1 dated 2 May 2023 to Protocol Version 2.0/

2 Study Overview

2.1 Study Design

This is a Phase I/II, open-label, single arm study to evaluate the PK, safety, and tolerability of BDQ given in combination with an individualized rifampin-resistant tuberculosis (RR-TB) therapy in infants, children, and adolescents with RR-TB disease, living with or without HIV.

Sample Size: Up to 84 participants total (24 for Cohort 1; 30 for Cohorts 2; 30 for Cohort 3) to achieve 54 evaluable participants (18 per age cohort):

Cohort 1: Age \geq 6 to < 18 years

Cohort 2: Age \geq 2 to < 6 years

Cohort 3: Age \geq 0 to < 2 years

Study Treatment and Duration: BDQ given as part of an individualized RR-TB treatment regimen for 24 weeks. For participants living with HIV, BDQ will be given in combination with an acceptable antiretroviral (ARV) therapy regimen initiated at least two weeks prior to enrollment.

Cohort	Age and Weight	BDQ Dosing
Cohort 1 up to 24 participants to achieve 18 evaluable (approximately nine in each weight band)	≥ 6 to < 18 years ≥ 30 kg	Participants ≥ 30 kg: 400 mg once per day through the intensive PK sampling visit*, then 200 mg three times per week on Monday, Wednesday, and Friday through the Week 24 visit
	≥ 6 to < 18 years ≥ 15 to < 30 kg	
Cohort 2 up to 30 participants to achieve 18 evaluable	≥ 2 to < 6 years > 7 kg	Participants > 7 to < 30 kg 200 mg once per day through the intensive PK sampling visit*, then 100 mg three times per week on Monday, Wednesday, and Friday through the Week 24 visit
Cohort 3 up to 30 participants to achieve 18 evaluable	≥ 0 to < 2 years ≥ 3 kg	Participants ≥ 3 to ≤ 7 kg: 100 mg once per day through the intensive PK sampling visit*, then 50 mg three times per week on Monday, Wednesday, and Friday through the Week 24 visit

*Intensive PK sampling will be performed at the Week 1 or Week 2 visit following receipt of at least 14 and no more than 17 BDQ daily doses, including any non-study BDQ doses taken prior to study entry.

2.2 Study Objectives

2.2.1 Primary Objectives

- Determine the BDQ doses that achieve similar weekly exposure (area under the curve (AUC)) of BDQ compared to adults taking BDQ at the current standard recommended dose.
- Evaluate the safety and tolerability of BDQ over a 24-week dosing period.

2.2.2 Secondary Objectives

- Evaluate the PK of BDQ over the 24-week dosing period, by HIV status.
- Describe the long-term safety and tolerability of BDQ over a 96-week total follow-up period, by HIV status.
- Describe BDQ concentrations following BDQ discontinuation and through 72 weeks after BDQ discontinuation, by HIV status.
- Describe the RR-TB treatment response up to 96 weeks from initiation of the study, by HIV status.

2.3 Overview of Sample Size Considerations

At least 54 and up to 84 participants will be enrolled in the study across three age cohorts, as follows:

- Cohort 1: ≥ 6 to < 18 years of age at enrollment
- Cohort 2: ≥ 2 to < 6 years of age at enrollment
- Cohort 3: ≥ 0 to < 2 years of age at enrollment

Up to 24 participants in Cohort 1, up to 30 participants in Cohort 2, and up to 30 participants in Cohort 3 will be enrolled to achieve at least 18 evaluable participants in each cohort. In Cohort 1, up to 12 participants will be enrolled in each of the two weight bands (15 to < 30 kg and ≥ 30 kg) to achieve approximately nine evaluable participants in each weight band.

Participants are considered PK-evaluable if they have completed the intensive PK sampling collection and have at least one sample with measurable BDQ and M2 concentrations. Participants will be assessed by the Core Team for evaluability once PK data from the intensive PK visit are available. Regardless of evaluability, the safety population for this study will include all participants who receive at least one dose of study drug.

Non-evaluable participants will be replaced unless the maximum accrual of 24 participants in Cohort 1 and 30 participants in Cohorts 2 and 3 is already achieved. It is possible for the maximum number of participants to be enrolled in a cohort and not achieve the required 18 evaluable participants; however, the sample size per cohort was determined to accommodate loss of participant data due to non-evaluability or loss to follow-up.

The sample size is primarily based on PK considerations. Clinical trial simulations were performed to ensure a sample size able to provide precise enough estimates of apparent clearance as specified by the US Food and Drug Administration (FDA) criteria for pediatric trials. Since BDQ exposure over long-term administration primarily is determined by the apparent clearance, the first point implies that the primary objective of the study (to determine BDQ doses for children that achieve similar weekly exposure as adults taking BDQ at the current standard recommended dose) can be fulfilled.

2.4 Overview of Monitoring

2.4.1 Interim Monitoring

There will be two interim analyses of PK and safety data for each age cohort, for a particular dosing scheme, during the dose-finding phase. The first will occur when six participants under the current BDQ dosing scheme have completed their intensive PK sampling at the Week 1 or Week 2 visit (see Sections 6.3 and 6.4 of the protocol). If the first six participants have acceptable PK and safety profiles, as evaluated by the Core Team, a second interim analysis will occur when 12 participants under the current BDQ dosing scheme have completed their intensive PK sampling.

During each interim analysis, the safety data will be considered “unacceptable” if the following conditions are met, as assessed by the Core Team (*only among evaluable participants in the cohort under evaluation for the current dosing scheme*):

- 1) Any fatal or life-threatening adverse event (AE) assessed by the Core Team to be at least possibly related to study drug occurs.
- 2) For N=6: At least two participants experience a grade 3 or non-life-threatening grade 4 AE assessed by the Core Team as at least probably related to study drug.
- 3) For N=12: At least three participants experience a grade 3 or non-life-threatening grade 4 AE assessed by the Core Team to be at least probably related to study drug.
- 4) For N=18: At least four participants experience a grade 3 or non-life-threatening grade 4 AE assessed by the Core Team to be at least probably related to study drug.

The safety data will be reviewed concurrently with PK data and whether PK criteria are met or not.

NOTE: At the time of finalization of this document, all planned interim PK and safety analyses for all cohorts have been completed.

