In addition, if possible, a primary evaluation of safety across the 24 weeks of study treatment will be performed on the data from participants who initiated the final recommended BDQ dose for a given cohort and remained on that dose for the 24-week period or have left the study or had a dose modification due to safety failure prior to 24 weeks of exposure (in which case the participant will be analyzed as a failure). Note that such an analysis may not be possible, since the PK modeling procedure which will determine the final recommended dose will not guarantee that any participant, or an adequate number of participants, be on that dose. However, secondary safety analyses will include all safety data collected from first participant exposure to the end of the study, with results broken down by dose. This will include data representing the final implemented dose for each cohort, as well as data gathered during the dose finding stage, which may represent exposure to doses which have failed.

Given that the modest sample sizes within cohorts will provide limited power for statistical tests of differences across age cohorts, only very large apparent effects would be statistically significant. Interpretation of differences across cohorts will depend upon whether these differences are great enough to be considered to be clinically significant. If no such differences are observed, then the clearest interpretation of the findings will come from the aggregated data, where analyses will have the greatest statistical precision. However, if results vary across cohorts to a clinically important extent, interpretation of results should consider the age differences and potential treatment differences represented by this stratification factor.

The proportions of participants meeting each of the endpoints which would trigger an *ad hoc* SMC review will be presented descriptively. Details concerning the analyses will be included in a separate analysis plan.

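### The interim acceptability verdict counts only PK-evaluable children, so a toxicity that prevents intensive PK sampling falls outside it; the three safety populations in SAP 2.3, 2.4.1 and 2.4.2 need reconciling, with one retrospective check

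*SAP*

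**What the plan says.** SAP 2.4.1 lists four conditions that make interim safety data unacceptable. One is any fatal or life-threatening event at least possibly related to study drug. The other three are counts of participants with a grade 3 or non-life-threatening grade 4 event at least probably related: 2 at N=6, 3 at N=12 and 4 at N=18. All four are assessed "only among evaluable participants in the cohort under evaluation for the current dosing scheme".

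SAP 2.3 supplies the only definition of evaluable: "Participants are considered PK-evaluable if they have completed the intensive PK sampling collection", with at least one measurable sample. The dosing table in SAP 2.1 places that sampling "following receipt of at least 14 and no more than 17 BDQ daily doses", and doses taken before study entry count. SAP 2.3 also says "Non-evaluable participants will be replaced unless the maximum accrual of 24 participants in Cohort 1 and 30 participants in Cohorts 2 and 3" has been reached.

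Two other statements use a different population. SAP 2.3: "Regardless of evaluability, the safety population for this study will include all participants who receive at least one dose of study drug". SAP 2.4.2 repeats the 2/6, 3/12 and 4/18 counts as SMC notification triggers for participants within a cohort, without mentioning evaluability. Its rule for related fatal or life-threatening events has no such limit either.

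A note in SAP 2.4.1 records that all planned interim analyses are complete.

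**The concern.** Evaluability here can depend on the outcome being monitored. A child who dies or stops for toxicity before intensive sampling cannot be PK-evaluable, so the event that ought to weigh against the dose also removes the child from the count. Replacement then restores N with a child who may have had no event. The direction is fixed: adding an omitted event back can only raise the count, so leaving it out can only favour the dose.

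At stake is what can be said about the doses carried forward. If any dosed child was non-evaluable because of a related toxicity, the interim verdict for that cohort and dosing scheme rests on a selected group. The documents do not say whether this happened.

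**Working it through.** **Plan's own figures.** Evaluable target: 3 × 18 = 54. Accrual caps: 24 + 30 + 30 = 84. Both agree with SAP 2.3. The documents give no operating characteristics for the safety rules, so there is nothing further to reproduce.

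**Room for replacement.** The caps ("Up to 24 participants in Cohort 1, up to 30 participants in Cohort 2, and up to 30 participants in Cohort 3") less 18 leave 6 places in Cohort 1 (6/24 = 25%) and 12 in each of Cohorts 2 and 3 (12/30 = 40%). No limit is stated on how many may be used for children lost to toxicity.

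**Inputs for the rule's behaviour.**
- From SAP 2.4.1: thresholds 2/6, 3/12 and 4/18.
- Assumed, not in the documents: p, the true rate of qualifying grade 3/4 events, and f, the share of those events that come before sampling and also prevent it.
- Simplification: early toxicity is the only cause of non-evaluability.

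**Event rate among evaluable children** = p(1 − f) / (1 − pf). At p = 0.25:
- f = 0: 0.25
- f = 0.25: 0.1875 / 0.9375 = 0.20
- f = 0.50: 0.125 / 0.875 = 0.143

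**Chance of meeting the rule** = binomial upper tail at that rate. For N=6:
- f = 0: 1 − 0.75^6 − 6 × 0.25 × 0.75^5 = 1 − 0.178 − 0.356 = 0.466
- f = 0.50: 1 − (6/7)^6 − 6 × (1/7) × (6/7)^5 = 1 − 0.397 − 0.397 = 0.207

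**Comparison.** The same thresholds are applied with the lost children's events added. The number lost before the nth evaluable child, K, is negative binomial: P(K = k) = C(n+k−1, k) a^k (1−a)^n, with a = pf. Each lost child adds one event.

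| p = 25% | N=6 | N=12 | N=18 |
|---|---|---|---|
| f = 0, either count | 46.6% | 60.9% | 69.4% |
| f = 25%, evaluable only | 34.5% | 44.2% | 49.9% |
| f = 25%, lost events added | 48.8% | 63.8% | 72.5% |
| f = 50%, evaluable only | 20.7% | 24.0% | 25.0% |
| f = 50%, lost events added | 51.1% | 66.6% | 75.5% |

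The added-events rows exceed the f = 0 row slightly because more than N children are then counted against an unchanged threshold.

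**Range over p, evaluable only, f = 0 → f = 50%.**

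| p | N=6 | N=12 | N=18 |
|---|---|---|---|
| 10% | 11.4% → 3.6% | 11.1% → 2.2% | 9.8% → 1.3% |
| 20% | 34.5% → 13.7% | 44.2% → 14.1% | 49.9% → 13.2% |
| 30% | 58.0% → 28.7% | 74.7% → 35.8% | 83.5% → 39.6% |
| 40% | 76.7% → 46.6% | 91.7% → 60.9% | 96.7% → 69.4% |

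If f = 0 there is no effect at any p.

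**The case against.** A reader might infer that an early death is simply dropped, the child replaced, and the study carries on unaware. The documents do not support that. Under SAP 2.4.2, a fatal or life-threatening event judged at least possibly related by the site investigator and/or the Core Team pauses accrual and brings in the SMC, whether or not the child was evaluable. That attribution test is wider than the one in 2.4.1, which uses the Core Team's assessment alone. Grade 3/4 events have their own SMC notification, and any other event or trend of concern can also go to the SMC. So the omission affects the 2.4.1 verdict, not oversight as a whole. Two gaps remain. The grade 3/4 route only notifies the SMC, and it does not say whether N counts evaluable or all dosed children.

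A reader might also infer that these events go unreported. They do not. SAP 4.1 plans listings of all events of grade 3 or higher, secondary analyses of all safety data by dose, and a descriptive summary: "The proportions of participants meeting each of the endpoints which would trigger an" ad hoc SMC review. SAP 4.3 adds a supplementary set of everyone exposed. The primary analysis set in SAP 4.3 has no PK-evaluability condition and treats toxicity discontinuations as failures for the relevant outcome. What is missing is a check of the interim verdicts themselves.

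Three further points stand. The size is hypothetical: f requires an event that is both early and prevents sampling, and pre-entry doses can shorten the on-study window. Rewording a rule whose analyses are complete would change nothing by itself, and counting all dosed children gives an N above 6, 12 or 18 for which no threshold is stated. Finally, SAP 2.4.1 says evaluable where 2.3 says PK-evaluable, and protocol Sections 6.3, 6.4 and 9.5.2, which were not available for this review, may define the term differently.

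**Conclusion.** The point holds for the formal interim verdict only. As written, SAP 2.4.1 can omit a related toxicity that prevents intensive PK sampling, and the omission can only favour the dose. SAP 2.3, 2.4.1 and 2.4.2 use different or unstated populations for the same safety question.

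The size is unknown because the documents report neither the event rate nor how many children were non-evaluable, or why. Under the assumed 25% rate, the loss in the chance of meeting the rule at N=6, 12 and 18 is 12.1, 16.7 and 19.5 percentage points if a quarter of events are early and prevent sampling (46.6 − 34.5, 60.9 − 44.2, 69.4 − 49.9). It is 25.9, 36.9 and 44.4 points if half are (46.6 − 20.7, 60.9 − 24.0, 69.4 − 25.0). If no child was lost to sampling through toxicity, every verdict stands unchanged. Nothing in the documents shows that an unsafe dose was passed.

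**What to change.** 1. Reconcile the populations in SAP 2.3, 2.4.1 and 2.4.2, checking them against protocol Sections 6.3, 6.4 and 9.5.2. State what evaluable means for the interim safety criteria and whom N counts in the SMC triggers. If the protocol already defines a separate safety evaluability, one clarifying sentence closes this part.
2. Because the interims are complete, add one table from existing data, by cohort and dosing scheme. For each N at which the criteria were applied, give the number of dosed but non-evaluable children, the reasons, their qualifying related events, and whether the verdict would change if those events were added to the count against the stated thresholds. Present it as a sensitivity check, noting that the thresholds were set for N of 6, 12 and 18.
3. Report the table beside the SMC-trigger proportions planned in SAP 4.1, and inform the SMC of any verdict that changes.

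The cost is a short clarification and one table; no new data are needed. The downside is that a past acceptability verdict may look less favourable.
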